## 6. GENERAL CONSIDERATIONS

Data will be summarized descriptively (frequency and percentage for categorical data and mean, standard deviation [SD] and range for continuous data, unless specified otherwise). In summary tables for categorical data for which categories are defined on the eCRF, all categories will be presented as specified, even if the participants count within that category is zero. All analyses will be provided separately for each age groups 18 to 64 years of age and for 65 years of age or above.

Unless otherwise specified, all data collected during the trial will be presented in listings for the ENR.

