3.0 OBJECTIVES, AND ENDPOINTS

Objectives	Endpoints (Population Summary)
Primary	

Immunogenicity:
 
To evaluate whether the monovalent influenza A/Astrakhan/3212/2020-like (H5N8) virus vaccine containing 3.75 µg, or 7.5 µg of HA with AS03_A or AS03_B elicits a HI response to the vaccine-homologous virus that meets or exceeds the US Food and Drug Administration, Center for Biologics Evaluation and Research immunogenicity criteria at the Day 43 visit.
	
Humoral immune response in terms of:
 
 • Vaccine-homologous HI titers at Day 43 (i.e., GMT). • Vaccine-homologous HI titers increase at Day 43 compared to pre-vaccination (i.e., GMFR). • SP defined as titer $\geq 1:40$ at Day 43 (percentage of participants meeting SP criteria).

Safety:
 
To evaluate the safety and reactogenicity of the different vaccine formulations through the Day 43 visit and SAEs and pIMDs through Day 43 and also to 6 months post dose 2
	
 • Occurrence of each solicited administration site event during a 7-day follow-up period (i.e., day of vaccination and 6 subsequent days) after each vaccination (percentage of participants with occurrence). • Occurrence of each solicited systemic event during a 7-day follow-up (i.e., day of vaccination and 6 subsequent days) after each vaccination (percentage of participants with occurrence). • Occurrence of toxicity grade increase in either hematology or biochemistry laboratory tests 7 days after each vaccination (percentage of participants with change from baseline). • Occurrence of unsolicited AEs for 21 days (i.e., day of vaccination and 20 subsequent days) after each vaccination (percentage of participants with occurrence). • Occurrence of MAEs for 21 days (i.e., day of vaccination and 20 subsequent days) after each vaccination and also through 6 months post dose 2 (percentage of participants with occurrence). • Occurrence of SAEs until Day 43 and also 6 months post dose 2 (percentage of participants with occurrence). • Occurrence of pIMDs until Day 43 and also 6 months post dose 2 (percentage of participants with occurrence).

Objectives	Endpoints (Population Summary)
Secondary	

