9.4.1 General Considerations

All analyses will be provided separately for each age subgroup.

Derived and transformed data:

- Immunogenicity at a visit (Note: The lower limit of quantitation (LLOQ) is defined by the laboratory before the analysis and will be specified in the clinical study report).
 - A seronegative participant is a participant whose titer is below the LLOQ.
 - A seropositive participant is a participant whose titer is greater than or equal to the LLOQ.
 - Seroprotection is defined as an HI titer $\geq 1:40$.
 - SPR is defined as the percentage of participants with an HI titer $\geq 1:40$.
 - HI seroconversion is defined as a post-vaccination titer $\geq 1:40$ in the serum of participants with pre-vaccination titer below 1:10 or as a ≥ 4 -fold rise in post-vaccination HI titer with pre-vaccination titer $\geq 1:10$.

- SCR is defined as the percentage of participants who seroconvert post-vaccination.
- MN vaccine response (VR) is defined as titer $\geq 4 \times$ LLOQ for participants with pre-vaccination titer below LLOQ or as a ≥ 4 -fold increase in MN titer for participants with pre-vaccination titer \geq LLOQ.
- Vaccine response rate (VRR) is defined as the percentage of participants with vaccine response.
- Geometric Mean Titer (GMT) calculations are performed by taking the anti-log of the mean of the log concentration/titer transformations. Values for the concentrations/titers below the LLOQ will be assigned half the LLOQ for the purpose of GMT computation.
- Handling of missing data: for a given participant and a given immunogenicity measurement, missing or non-evaluable measurements will not be replaced.
- The primary and secondary HI immunogenicity analyses will be based on the PPS.
- The MN immunogenicity analyses will be based on the PPS.

- Reactogenicity and Safety – Handling of missing data: For safety analyses, participants who missed reporting symptoms (solicited or unsolicited) or concomitant medications will not be imputed. Therefore, the analysis of the solicited symptoms based on the DS will include only participants/doses with documented safety data (i.e., symptom screen/sheet completed). Further details on the handling of missing data will be described in the SAP.

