9.4.3.2 Safety

The analysis of reactogenicity will be based on the DS while the analysis of other safety endpoints such as unsolicited events will be based on the ES. The following analysis will be generated for each vaccine group.

Solicited administration site and systemic endpoints

The following summaries will be generated for any grade ([Table 13](#)), grade ≥ 2 , grade ≥ 3 , medically attended, ongoing after day 7:

- Occurrence of at least one solicited administration site event during a 7-day follow-up period (i.e., day of vaccination and 6 subsequent days) after each vaccination and overall.
- Occurrence of at least one solicited systemic event during a 7-day follow-up period (i.e., day of vaccination and 6 subsequent days) after each vaccination and overall.
- Duration of each solicited AE starting on the day of vaccination or on one of the 6 subsequent days will be summarized after each vaccination and overall.

Frequencies and percentages of participants experiencing each event will be presented for each vaccination and across vaccinations with Clopper-Pearson exact 95% CIs.

If a solicited event occurs more than once for a participant, it will be counted in the summary only once for each level of summarization, according to the maximal severity.

Laboratory endpoints

The percentage of participants with an increase in laboratory toxicity grading after each vaccination and across vaccinations will be provided with Clopper-Pearson exact 95% CIs.

This will be done for each safety laboratory test and across laboratory tests for exposed participants with safety laboratory results available after vaccination.

Unsolicited AE and MAE endpoints

- Occurrence of unsolicited AEs within 21 days (day of vaccination and 20 subsequent days) after each vaccination and overall.
- Occurrence of MAEs within 21 days (day of vaccination and 20 subsequent days) after each vaccination and also through 6 months post dose 2.

SAE/pIMD endpoints

- Occurrence of SAEs and pIMDs up to Visit 5 (Day 43) and also through 6 months post dose 2.

The original verbatim terms used by investigators to identify AEs in the eCRFs will be mapped to preferred terms (PTs) using the Medical Dictionary for Regulatory Activities (MedDRA). The AEs will then be grouped by Medical Dictionary for Regulatory Activities PTs into frequency tables according to system organ class.

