## 2.4. Estimands

The primary, and secondary estimands to support regulatory decisions are described in the following table and are applicable for young adults (18-64 years of age) and older adults(65 years of age or older) separately:

	Study Intervention	Analysis set	Variable (or endpoint)	Intercurrent events (ICEs)		Population level summary
				Description	Handling strategy	
Primary	The study intervention will be defined by the first dose administered	PPS	Titers for vaccine-homologous HI titers at day 43	1. Study vaccination not administered as per protocol 2. Prohibited medication or intercurrent medical condition prior to Visit 4 (Day 43) 3. Blood sample taken out of window at Day 43 See section 5.6 and 9.2 for further details.	Participants will be excluded from the analysis at Day 43 See section 5.6 and 9.2 for further details on handling the intercurrent events and protocol deviations	GMTs with 2-sided 95% CI for vaccine-homologous HI titers at Day 43 for each study intervention group using ANCOVA. The ANCOVA model includes dose group effect as a fixed effect and log-transformed titer pre-dose 1 (Day 1) as a covariate.
Primary	The study intervention will be defined by the first dose administered	PPS	GMFR for vaccine-homologous HI titers at day 43	Refer to first primary endpoint	Refer to first primary endpoint	GMFR, with ANCOVA derived 95% CIs, for vaccine-homologous HI titers at Day 43 for each study intervention group. The ANCOVA model includes dose group effect

Document: \\ieedc-vnasc01\BIOSdata\GSK\H5N8(Flu)\HAB99808\Biostatistics\Documentation\SAP\SAP\SAP v5.0\GSK H5N8-219833\_SAP\_v5.0\_19AUG2024.docx

Author: PPD

Version Number: 5.0

Version Date: 19AUG2024

Template No.: CS\_TP\_BS016 Revision 7

Reference: CS\_WI\_BS005

Effective Date: 01Nov2021

	Study Intervention	Analysis set	Variable (or endpoint)	Intercurrent events (ICEs)		Population level summary
				Description	Handling strategy	
						as a fixed effect and log-transformed titer pre-dose 1 (Day 1) as a covariate.
Primary	The study intervention will be defined by the first dose administered	PPS	HI SP at day 43, defined as vaccine-homologous H5N8 HI titer $\geq 1:40$	Refer to first primary endpoint	Refer to first primary endpoint	SPR, defined as percentage of participants meeting SP definition, will be reported with Clopper-Pearson exact 2-sided 95% CIs at Day 43 for each study intervention group.

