### **5.4. Exposed Set [ES]**

Participants who received a study intervention. For analyses and displays based on ES, participants will be classified according to study intervention administered at dose 1 (i.e., study intervention actually received).

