## 7.5. Examination of Subgroups

All endpoints will be produced separately for each age group: 18 to 64 years of age and  $\geq$  65 years of age.

---

Document:	\ieedc-vnasc01\BIOSdata\GSK\H5N8(Flu)\HAB99808\Biostatistics\Documentation\SAP\SAP\SAP\SAP v5.0\GSK H5N8-219833_SAP_v5.0_19AUG2024.docx		
Author:	PPD	Version Number:	5.0
		Version Date:	19AUG2024

Template No.: CS\_TP\_BS016 Revision 7

Reference: CS\_WI\_BS005

Effective Date: 01Nov2021

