#### **16.1.4. Serious Adverse Events**

SAEs will be summarized and listed as:

- The number and percentage of participants, with exact 95% CIs, with at least one report of SAE with onset after each vaccine administration up to Day 43 and up to study end (i.e., 6 months post-last vaccination) will be summarized.
  - This summary will be repeated for:
    - Causally related SAEs
    - Fatal SAEs
    - Causally related fatal SAEs
    - All SAEs will be included in a listing.

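### The safety objective is set by formulation, but the SAP text specifies safety estimates only by age group and names no ages-combined summary per formulation

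*SAP*

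**What the plan says.** Protocol 3.0 states the primary safety objective by product: "To evaluate the safety and reactogenicity of the different vaccine formulations through the Day 43 visit". SAP 2.1 repeats it.

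The analysis rule is by age:

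- Protocol 9.4.1: "All analyses will be provided separately for each age subgroup".
- SAP 6: "All analyses will be provided separately for each age groups 18 to 64 years of age and for 65 years of age or above". SAP 3.1 says the same.
- SAP 7.5: "All endpoints will be produced separately for each age group: 18 to 64 years of age", and the sentence goes on to the older group.
- SAP 2.4: the estimands, including every primary safety estimand in the table, "are applicable for young adults (18-64 years of age) and older adults(65 years of age or older) separately".

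None of these makes an exception for safety.

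The safety sections themselves are silent on age. Protocol 9.4.3.2 says "The following analysis will be generated for each vaccine group". SAP 5.4 says "For analyses and displays based on ES, participants will be classified according to study intervention administered at dose 1". SAP 16.1.4 promises "The number and percentage of participants, with exact 95% CIs, with at least one report of SAE with onset after each vaccine administration". SAP 16 does use the word overall, but directly after each vaccination, so it most naturally means across the two doses. When the SAP wants a total over groups, as for disposition (9.1) and deviations (9.2), it says so by naming the study groups first.

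**The concern.** The objective asks about four formulations, and the written rule delivers eight age-by-formulation cells. No sentence connects the two levels. A programmer following the text would produce an exact interval for 65 people in each cell, and would have no instruction to produce one for the 130 who received a given formulation.

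This matters most for uncommon events. An empty SAE or pIMD cell of 65 is weak evidence. The laboratory tables are weaker still, because SAP 16.2 restricts post-vaccination tests to the first half of each cell. The ages-combined estimate that matches the objective would use data already collected, at about twice the precision for uncommon events.

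**Working it through.** **Inputs.** SAP 2.5: 65 per age subgroup in each of 4 dose groups, 520 in total. Protocol 4.1: about 130 per dose group. SAP 6.5: Clopper-Pearson intervals, 95% by default. SAP 16.2: laboratory tests in the first 50% of each cell, so 65 × 0.5 = 32.5, or 32 to 33 people. Assumption: every planned participant is exposed.

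**The plan's own figures.** The documents give no precision figure for safety. Their only power figures concern seroprotection, and these reproduce. The smallest count whose Clopper-Pearson lower limit reaches the criterion is 42 of 50 (70%) and 34 of 45 (60%). Exact binomial power is 0.9421 at a true rate of 90% and 0.8259 at 80%. The product is 0.778, matching the stated 77.8%. With 85% in the older group it is 0.9421 × 0.9698 = 0.914, matching 91.4%.

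**Safety precision.** With no events among n people, the two-sided 95% Clopper-Pearson upper limit is U = 1 − 0.025^(1/n). For n = 65, U = 1 − 0.025^(1/65) = 5.5%. The chance of at least one event at true risk p is 1 − (1 − p)^n. For p = 0.5% and n = 65 that is 1 − 0.995^65 = 27.8%.

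| Level | n | Upper limit, 0 events | Upper limit, 1 event | Chance of ≥1 event at 0.5% | Chance at 0.1% |
|---|---|---|---|---|---|
| Age-by-formulation cell | 65 | 5.5% | 8.3% | 27.8% | 6.3% |
| Formulation, ages combined | 130 | 2.8% | 4.2% | 47.9% | 12.2% |
| All exposed | 520 | 0.71% | 1.07% | 92.6% | 40.6% |

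For laboratory tests, zero events leaves an upper limit of 10.9% at n = 32 and 10.6% at n = 33. Combining ages within a formulation would bring that subset to about 65 and the limit to about 5.5%.

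The zero-event limit therefore falls by a factor of 5.52/2.80, about 2, from cell to formulation, and by 5.52/0.707, about 8, from cell to everyone.

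**The case against.** The case on the other side is substantial.

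- **Separately is not exclusively.** No sentence bars a combined table, and SAP 7.5 sits under a subgroup heading; subgroup tables usually accompany main ones.
- **Parts of the text can be read as per formulation.** Protocol 9.4.3.2 speaks of vaccine groups. SAP 7.2 counts about 130 per study intervention group. SAP Appendix 1 sets four output labels, not eight. SAP 10 lists age category as a demographic row, which is informative only in a table that pools ages.
- **The layouts cannot be checked.** SAP 4.3 and 8 refer to mock shells and templates that are not in the text reviewed.
- **Age-specific results are deliberate.** Protocol 4.2 gives differences in safety profile by age as part of the design rationale.
- **No data are lost.** The age strata do not overlap, so a reader can add counts and recompute the interval. SAEs and pIMDs are also listed individually.

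All of this limits what can be claimed. A reader might infer that safety is reported only by cell and never by formulation. The documents do not establish that, because the wording is open and the templates are unseen. A reader might also infer that the objective calls for an all-participant estimate. It does not: it names the formulations and sets no rare-event target. Nor is it right that the layout is what prevents rare events from being bounded. Sample size does that, since even 520 people have only about a 41% chance of showing a 1-in-1,000 event.

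What the objection does not supply is an instruction to combine ages. The age rule is repeated across both documents and built into the safety estimands. If the templates do pool, the SAP text should say so. If they do not, the estimate matching the objective is left to the reader's arithmetic rather than prespecified.

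**Conclusion.** There is a gap between a safety objective set by formulation and a safety analysis specified by age group, with no ages-combined summary named in the text. The cost is precision: with zero events the upper limit is 5.5% at the cell level against 2.8% at the formulation level, and about 10.6% to 10.9% against about 5.5% for laboratory tests. A total over all exposed would reach 0.71%, but that goes beyond what the objective requires.

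These figures assume all 65 per cell are exposed and, for laboratory tests, that half of each cell is tested; fewer would widen the limits. The finding rests on the SAP and protocol text, not on the templates. Safety is descriptive, with no between-group comparisons (SAP 16), so no planned decision depends on it. It is a worthwhile and cheap improvement, not a flaw that undermines the trial.

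**What to change.** In SAP 7.5 and 16, keep the age-specific safety tables and state that each also carries one column per formulation with both ages combined, with exact 95% intervals. Optionally, add a descriptive total over all exposed participants for SAEs and pIMDs. If the templates already contain such columns, one sentence in the SAP is enough.

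The cost is extra table columns from data already planned. The downside is interpretive. Ages-combined columns average over the designed 50:50 age split, and the total also averages over four formulations with no control arm. Both should therefore stand beside the age-specific results, labelled descriptive, and not replace them. Sample size, power, hypotheses and success criteria stay as they are.

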### 6.1. Reference Start Date and Study Day

Study Day will be calculated from the reference start date and will be used to show start/stop day of assessments and events. It will appear in every listing where an assessment date or event date appears.

In general, the reference start date is defined as the day of the first dose of each study vaccination, which is Day 1 for all participants.

- If the date of the event is on or after the reference date, then:
  - Study Day = (date of event – reference date) + 1.
- If the date of the event is prior to the reference date, then:
  - Study Day = (date of event – reference date).

For some domains such as AE start, medication start day the reference date is the date of last study vaccination, and this is complemented by the number of previous study vaccinations.

In the situation where the event date is partial or missing, refer to [APPENDIX 2](#).

### 6.2. Baseline

Unless otherwise specified, baseline is defined as the last non-missing measurement taken prior to the first study intervention (including unscheduled assessments) and will be referenced as pre-vaccination. In the case where the last non-missing measurement and the reference start date coincide, and time is not collected, that measurement will be considered pre-vaccination. If time is not collected, Day 1 (Visit 1) assessments are assumed to be taken prior to first dose and used as pre-vaccination values.

---

Document: \\ieedc-vnasc01\BIOSdata\GSK\H5N8(Flu)\HAB99808\Biostatistics\Documentation\SAP\SAP\SAP v5.0\GSK H5N8-219833\_SAP\_v5.0\_19AUG2024.docx  
Author: PPD Version Number: 5.0  
Version Date: 19AUG2024

Template No.: CS\_TP\_BS016 Revision 7

Reference: CS\_WI\_BS005

Effective Date: 01Nov2021

## 6.3. Retests, Unscheduled Visits and Early Termination Data

In general, for by-visit summaries, data recorded at the nominal visit will be presented. Repeat safety laboratory assessments at ad-hoc visits will not be included in by-visit summaries. The safety laboratory assessments at ad-hoc visits will be presented in listings.

## 6.4. Windowing Conventions

Allowed time window for each visit will be performed as mentioned in “Schedule of Activities”, section 1.3 of protocol. Intervals between study visits are included in [Table B](#) and window conventions are included in

---

Document:	\ieedc-\vnasc01\BIOSdata\GSK\H5N8(Flu)\HAB99808\Biostatistics\Documentation\SAP\SAP\SAP\SAP v5.0\GSK H5N8-219833_SAP_v5.0_19AUG2024.docx		
Author:	PPD	Version Number:	5.0
		Version Date:	19AUG2024
Template No.:	CS_TP_BS016 Revision 7		
Effective Date:	01Nov2021		
Reference:	CS_WI_BS005		

**Table C.** In case vaccination or lab sample planned at a visit was made on another day, the same interval window will be used for the actual vaccination/lab sample date.

In protocol amendment 3.0 version the visit interval windows have been updated for Visit 1 → Visit 3 and Visit 3 → Visit 5, from 14-28 days to 14-35 days. The window visits have been extended due to the large number of participants whose Visit 3 or Visit 5 was out of window due to the enrolment hold. The Window convention in table C are updated accordingly.

Table B: Intervals between Study Visits

Interval	Planned visit interval	Allowed interval range
Screening → Visit 1	Up to 14 days	14 days
Visit 1 → Visit 2	7 days	7-9 days
Visit 1 → Visit 3	21 days	14-35 days
Visit 3 → Visit 4	7 days	7-9 days
Visit 3 → Visit 5	21 days	14-35 days
Visit 3 → Visit 6	180 days post dose 2	165-195 days

---

Document:	\\ieedc-vnasc01\BIOSdata\GSK\H5N8(Flu)\HAB99808\Biostatistics\Documentation\SAP\SAP\SAP v5.0\GSK H5N8-219833_SAP_v5.0_19AUG2024.docx
Author:	PPD
	Version Number: 5.0
	Version Date: 19AUG2024

Template No.: CS\_TP\_BS016 Revision 7

Reference: CS\_WI\_BS005

Effective Date: 01Nov2021

Table C: Window convention

Assigned Study Day	Visit label as per protocol	Visit assigned
Day 1	Visit 1	Visit 1 (Day 1)
Day 8	Visit 2	Visit 2 (Day 8-10)
Day 22	Visit 3	Visit 3 (Day 15-36)
Day 29	Visit 4	Visit 4 (Day 22-45)
Day 43	Visit 5	Visit 5 (Day 29-71)

## 6.5. Statistical Tests

The default significant level will be (5%); confidence intervals (CIs) will be 95%, unless otherwise specified in the description of the analyses.

CI for proportion will be based on exact Clopper-Pearson CI [[Section 18](#)].

The group adjusted geometric mean titers (GMT) ratio will be based on a back transformation of group contrast in an Analysis of Covariance (ANCOVA) model applied to the logarithm-transformed titers.

## 6.6. Common Calculations

GMT:

Distributions of antibodies are generally skewed to the right ([Section 18](#)). Therefore, prior to any statistical analysis that assumes normally distributed observations, titers will be log10-transformed. GMTs and their 95% CI are computed by exponentiating (base 10) the least squares mean and 95% CI of the log10 titers.

The GMT at visit i will be calculated using the following formula:

$$10^{\frac{\sum_{i=1}^n \log_{10}(t_i)}{n}}$$

---

Document: \\ieedc-vnasc01\BIOSdata\GSK\H5N8(Flu)\HAB99808\Biostatistics\Documentation\SAP\SAP\SAP\SAP v5.0\GSK H5N8-219833\_SAP\_v5.0\_19AUG2024.docx

Author: PPD Version Number: 5.0

Version Date: 19AUG2024

Template No.: CS\_TP\_BS016 Revision 7

Reference: CS\_WI\_BS005

Effective Date: 01Nov2021

GMT calculations are performed by taking the inverse logarithm of the mean of the  $\log_{10}$  titer transformations. Likewise the GMFR at visit  $i$  and associated CI will be calculated from the same formula with  $t_i$  replaced by  $t_i / t_1$ . Non-quantifiable titers will be converted as described in [Table D](#) for the purpose of GMT / GMFR calculation. Numerical serology results will be derived from the content of IS.ISORRES in the SDTM dataset. For all the assays available for the study, assay derivation rules are included in [Table D](#).

Table D: Assay Derivation Rules

IS.ISORRES	Derived value
“NEG”, “-”, or “(−)”	LLOQ/2
“POS”, “+”, or “(+)”	Value
“< value” and value is $\leq$ LLOQ	LLOQ/2
“> value” and value is $<$ LLOQ	LLOQ/2
“> value” and value is $\geq$ LLOQ	Value
“value” and value is $<$ LLOQ	LLOQ/2
“value” and value is $\geq$ ULOQ	ULOQ
“value” and value is $>$ ULOQ	ULOQ
All other cases	missing

Note: The Reverse Cumulative Distribution (RCD) generated will not use the upper limit of quantification (ULQ) values but the exact value if the exact value is greater than ULOQ.

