## 7.3. Missing Data

Missing data (missing, incomplete or partial dates, AE measurement [including missing AE severity and relationship], prior and concomitant medications and death date) will be handled as per [APPENDIX 2](#) of this SAP.

Missing immunogenicity data will not be imputed. Titers below LLOQ will be replaced by LLOQ/2 for the purpose of GMT computation. Titers above the ULOQ will be replaced by the ULOQ.

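### SAP Table D has no row for a plain numeric titer from LLOQ up to ULOQ; read literally, its last row sets such titers to missing in the primary GMT and GMFR

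*SAP*

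**What the plan says.** SAP 6.6 introduces Table D in three sentences that do not share one scope. The first is narrow: "Non-quantifiable titers will be converted as described in" Table D, for calculating GMT and GMFR. The next two are broad: "Numerical serology results will be derived from the content of IS.ISORRES in the SDTM dataset", and "For all the assays available for the study, assay derivation rules are included in" Table D.

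For a result that is a plain number, the table lists three conditions:
- below LLOQ, giving LLOQ/2;
- "and value is $\geq$ ULOQ", giving ULOQ;
- above ULOQ, again giving ULOQ.

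The last row, "All other cases", gives missing. For a result reported with a greater-than sign, the row "and value is $\geq$ LLOQ" returns the value itself, with no upper cap. The note under the table says the reverse cumulative curves use not the ULOQ "but the exact value if the exact value is greater than ULOQ".

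SAP 7.3 gives its own substitutions. "Titers below LLOQ will be replaced by LLOQ/2 for the purpose of GMT computation", and titers above ULOQ become ULOQ. It also says missing immunogenicity data are not imputed. Protocol 9.4.1 substitutes only below LLOQ.

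**The concern.** The ordinary result, a measured titer inside the quantifiable range, is the one case Table D omits. According to protocol Appendix 2 (section 10.2), the reported HI result is the geometric mean of two duplicate titers. In-range plain numbers are therefore the core of the data.

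Two adjacent rows, at or above ULOQ and above ULOQ, give the same output. One is redundant where an in-range row would be expected. Because the table ends in a catch-all, a program that follows it as a complete mapping sets in-range titers to missing without raising an error.

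The Day 43 HI GMT and GMFR are named primary endpoints (SAP 15.1.1). The ANCOVA in SAP 15.1.3 uses the Day 1 titer as covariate, so an in-range Day 1 titer set to missing would also remove that participant from the model. SAP 6.6 applies the table to all assays, so the MN GMTs have the same exposure.

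**Working it through.** The plan states no figure for this point, so there is none to reproduce. The check applies Table D row by row to the possible HI results.

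**Inputs.** Dilution range 1:10 to 1:10240, two-fold, in duplicate (protocol 10.2). Derivation rows from SAP 6.6. Substitution rules from SAP 7.3. LLOQ and ULOQ are not given, because protocol 9.4.1 leaves the LLOQ to the laboratory. The limits below are assumptions.

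**Step 1: the grid.** 10 × 2^k for k = 0 to 10 gives 10, 20, 40, 80, 160, 320, 640, 1280, 2560, 5120 and 10240, which is 11 steps.

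**Step 2: the literal rule for a plain number v.** v < LLOQ gives LLOQ/2; v ≥ ULOQ gives ULOQ; otherwise missing. When both limits lie on the grid, the number of steps set to missing is log2(ULOQ/LLOQ). For example, log2(10240/10) = 10 and log2(1280/40) = 5.

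| Assumed LLOQ | ULOQ 1280 | ULOQ 2560 | ULOQ 5120 | ULOQ 10240 |
|---|---|---|---|---|
| 10 | 7 of 11 | 8 of 11 | 9 of 11 | 10 of 11 |
| 20 | 6 of 11 | 7 of 11 | 8 of 11 | 9 of 11 |
| 40 | 5 of 11 | 6 of 11 | 7 of 11 | 8 of 11 |

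In every cell the only non-missing derived values are LLOQ/2 and ULOQ. These are counts of dilution steps, not of participants.

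**Step 3: averaged duplicates.** If duplicates agree or differ by one dilution, there are 11 + 10 = 21 possible results. The in-range results set to missing are 20 of 20 (limits 10 and 10240), 18 of 18 (20 and 10240), 18 of 18 (10 and 5120) and 16 of 16 (28 and 7240).

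**Step 4: effect on a GMT, illustration only.** Take ten results: <10, 10, 20, 40, 80, 160, 320, 640, 1280 and 10240, with limits 10 and 10240.
- Literal table: only <10 (set to 5) and 10240 remain. GMT = √(5 × 10240) = 226.3.
- In-range values kept: all ten remain. GMT = 130.0.

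**Step 5: the greater-than row.** A result of `>10240` is 10240 under Table D and ULOQ under SAP 7.3. The ratio 10240/ULOQ is 8, 4, 2 and 1 for ULOQ 1280, 2560, 5120 and 10240, or 0.90, 0.60, 0.30 and 0 on the log10 scale.

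**Step 6: after correction.** With a row that keeps a plain value from LLOQ to ULOQ inclusive, 0 of 11 steps are missing for all 12 pairs of limits in the table above.

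**The case against.** The strongest reply is that the intent is clear. The first scope sentence in SAP 6.6 confines the table to non-quantifiable titers. SAP 7.3 and protocol 9.4.1 replace only out-of-range values, which presupposes that the others stand. The literal reading would defeat the GMT analysis, and a nearly empty table would be obvious in a dry run. On this view it is a drafting slip already resolved by SAP 7.3.

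Much of that stands. The intended handling can be inferred, and nothing here shows that data were or will be lost. But the inference has to override the table. The two sentences after the narrow one derive numerical results from the raw result field and place the rules for all assays in Table D. The catch-all row has the form of a complete mapping. Neither SAP 7.3 nor protocol 9.4.1 states that in-range titers keep their value.

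A second reply is that the sentence limiting the conversion to GMT and GMFR is used here to spare the seroprotection rate, while its limit to non-quantifiable titers is not treated as decisive. The point is fair. It is a reason to claim no effect on seroprotection and to state the scope outright.

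A third is that the sizes rest on assumed limits, and that the greater-than mismatch vanishes if ULOQ is the top dilution. Both are correct. The conflict in the greater-than row still holds under either scope whenever the reported value exceeds ULOQ, since such a result is non-quantifiable on any reading.

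Finally, the defect rests on symbols in a machine-read table, so a transcription fault cannot be excluded.

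**Conclusion.** The concern holds as a specification error that should be fixed. As the table reads, every plain numeric titer with LLOQ ≤ value < ULOQ has no row and goes to missing.

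The consequence depends on scope: none under the narrow reading; under the broad reading, all in-range plain titers drop out of the primary GMT and GMFR. A share of participants cannot be given, because LLOQ and ULOQ are not stated. The step counts, 5 to 10 of 11, hold only for the assumed limits.

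The greater-than row conflicts with SAP 7.3 when the reported value exceeds ULOQ, by a factor of 1 to 8 for `>10240` over the assumed range of ULOQ.

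No effect on the confirmatory test is claimed. Success under SAP 7.4 depends only on the lower confidence limits of the seroprotection rates, those rates are defined on the HI titer, and the conversion is stated to be for GMT and GMFR.

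**What to change.** Check Table D against the source file first. If it reads as here:

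1. Replace the plain-number row for values at or above ULOQ with: plain value, LLOQ ≤ value ≤ ULOQ, gives value. Keep the row that sets a plain value above ULOQ to ULOQ.
2. Change the greater-than row so that a value from LLOQ to ULOQ gives that value and a value above ULOQ gives ULOQ, in line with SAP 7.3.
3. State in one sentence that the Table D derivations apply to GMT and GMFR. Leave as they are the use of exact values above ULOQ in the reverse cumulative curves and the separate LLOQ/2 rule for MN vaccine response in SAP 15.2.1.

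The cost is two rows in one SAP table and one sentence. Design and data collection are not affected.
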